5.2. Patient Withdrawal Criteria

A patient should be withdrawn from study treatment if, in the opinion of the Investigator, it is medically necessary, or if it is the wish of the patient. If a patient does not return for a scheduled

visit, every effort should be made to contact the patient. In any circumstance, every effort should be made to document patient outcome. Data to be collected at the end of study visit are described in the Schedule of Assessments (Table 7, Table 8, Table 9, Table 10, and Table 11). Patients will be followed for at least 28 days after the last dose of TRC105 study drug for adverse events. If the patient withdraws consent, no further evaluations should be performed, and no attempts should be made to collect additional data. Patients may be withdrawn for DLT, but DLT does not mandate withdrawal if the DLT resolves and can be treated (i.e., a first dose infusion reaction).

Patients will be withdrawn from treatment in the case of:

1. RECIST 1.1-defined disease progression. In cases where RECIST cannot be applied, progression should be based on unequivocal evidence of progressive disease sufficient to require a change in therapy.
2. A need for anticancer surgery, radiation, or for other anticancer therapy not specified in the protocol.
3. Lost to follow-up or noncompliant.
4. Any TRC105 dose delay > 2 days in cycle 1 (phase 1b only cohorts -1, 1, and 2 only)
5. Pregnancy. Pregnant patients should be followed for the duration of the pregnancy and the outcome of the pregnancy should be documented.
6. Arterial thrombosis of any grade (including cerebrovascular ischemia, cardiac ischemia/infarction, or peripheral or visceral arterial ischemia), grade 3 or 4 venous thrombosis (including pulmonary embolism), grade ≥ 2 intracranial hemorrhage, grade 3 or 4 non-CNS hemorrhage. Grade 2 non-CNS hemorrhage does not mandate withdrawal if the underlying condition is treatable. Grade 1 intracranial hemorrhage does not mandate withdrawal and may be treated with dose interruption if the patient is benefitting from treatment.
7. Missed study drug treatment for > 8 consecutive weeks (i.e., both TRC105 and axitinib dosing held if assigned to the combination arm or axitinib held if assigned to axitinib alone arm). However, patients assigned to the combination arm who cannot tolerate axitinib or TRC105 therapy and who demonstrate a response of complete response (CR), partial response (PR) or stable disease (SD) with the combination and are thought to benefit from continued single agent therapy may continue on study on TRC105 or axitinib alone.

6. TREATMENT OF PATIENTS

6.1. Description of TRC105 Study Drug

TRC105 is a genetically engineered human/murine chimeric monoclonal antibody directed against human CD105 found on the surface of proliferating endothelial cells.

6.1.1. Composition of TRC105

TRC105 is an IgG1, kappa immunoglobulin containing murine light- and heavy-chain variable region sequences and human constant region sequences. TRC105 has an approximate molecular weight of 148 kDa.

6.1.2. TRC105 Dose Level

Each patient will be dosed with 6, 8, 0, 15, or 20 mg/kg. **The maximum weight that should be used for purpose of dose calculation is 85 kg for women and 100 kg for men.** Thus, the maximum dose that should be given to a woman at the 6 mg/kg dose level is 510 mg, at the 8 mg/kg dose is 680 mg, at the 10 mg/kg dose is 850 mg, at the 15 mg/kg dose is 1275 mg, and at the 20 mg/kg dose is 1700 mg and the maximum dose that should be given to a man at the 6 mg/kg dose level is 600 mg, at the 8 mg/kg dose is 800 mg, at the 10 mg/kg dose is 1000 mg, at the 15 mg/kg dose is 1500 mg, and at the 20 mg/kg dose is 2000 mg. TRC105 is distributed according to lean body mass rather than overall body weight. Patients who are overweight would be at risk for high serum levels of TRC105 if the doses were not capped. 85 kg for women and 100 kg for men represent accepted maximum lean body masses for the two genders. The calculated dose of TRC105 can be rounded up or down to the nearest 1.0 mg; in the case of an increment of 0.5 mg the dose should be rounded up.

Weekly Dosing (refer to [Table 12](#)):

The first weekly TRC105 dose (cycle 1 day 1) will be split into two doses whereby 3 mg/kg is administered on cycle 1 day 1 and the balance is administered on cycle 1 day 4. The entire weekly dose of TRC105 (6, 8 or 10 mg/kg) is then given on cycle 1 day 8 and weekly thereafter and on days 1, 8, 15 and 22 of each subsequent 28 day cycle.

Every Two Week Dosing [refer to [Table 13](#) (15 mg/kg) or [Table 14](#) (20 mg/kg)]:

TRC105 can may be administered every two weeks starting with cycle 2 day 1 but **ONLY AFTER COHORT 3 & AND 4 IN THE PHASE 1B ARE COMPLETE AND THE & SPONSOR SENDS NOTIFICATION TO PROCEED WITH EVERY TWO WEEK DOSING.**

- Axitinib dosing will begin on cycle 1 day 1 and twice daily thereafter
- TRC105 will be administered weekly during cycle 1.
 - The first weekly TRC105 dose (i.e., 10 mg/kg) will be split into two doses whereby 3 mg/kg is administered on cycle 1 day 1 and the balance is administered on cycle 1 day 4.

-
- Starting on cycle 2 day 1 and beyond, TRC105 may be administered every two weeks on days 1 and 15

6.1.3. TRC105 Packaging and Labeling

TRC105 may be provided in one or more of the following presentations.

Phosphate Buffered Saline Formulation (7 mg TRC105/mL)

- 210 mg TRC105/30 mL single-use vial

20 mM L-Histidine/L-Histidine Monohydrochloride, 240 mM Trehalose,

0.01% Polysorbate 20 Formulation (25 mg TRC105/mL)

- 100 mg TRC105/4 mL single-use vial
- 200 mg TRC105/8 mL single-use vial
- 400 mg TRC105/16 mL single-use vial

6.1.4. TRC105 Storage and Shipping

TRC105 must be stored upright between 2 °C and 8 °C (36 °F to 46 °F) and protected from light.

6.1.5. TRC105 Preparation

TRC105 will be prepared in the pharmacy and diluted into normal saline using appropriate aseptic technique. TRC105 will be administered using an in-line 0.2 micron filter. No incompatibilities between TRC105 and polyvinyl chloride or polyolefin bags have been observed. Multiple vials will be required for a single dose. The following formulae should be used to calculate the volume of TRC105 to be added to normal saline:

- Patient weight (kg) × dose level (mg/kg) divided by TRC105 concentration (mg/mL) = volume of TRC105 (mL) to be administered.

The volume of TRC105 that is to be administered can be rounded up or down to the nearest 1.0 mL; in the case of an increment of 0.5 mL the volume should be rounded up. **The maximum weight that should be used for dose calculation in this study is 85 kg for women and 100 kg for men (note: there is not a weight restriction for enrollment purposes).** If the patient's weight changes by > 10% during the study, the dose of TRC105 will be recalculated. At that time a new baseline weight will be established such that subsequent weight changes by >10% from the new baseline weight would require further recalculation of the TRC105 dose. The calculated volume of TRC105 will be diluted with normal saline. Appropriate judgment should be exercised in withdrawing an adequate amount of saline necessary to permit injection of the appropriate volume of antibody into a normal saline bag in accordance with the dose needed. The final TRC105 concentration must be between 0.6 mg/mL and 10 mg/mL. The prepared TRC105 must be gently inverted several times in order to ensure a homogeneous solution. The diluted infusion solution of TRC105 should be used within 8 hours of preparation if stored at room temperature, or within 24 hours of dilution if stored at 2° to 8°C (36° to 46°F). The expiration time should be labeled on the bag. If the diluted infusion solution of TRC105 cannot be infused within 8 hours of preparation (i.e., the prepared infusion is at room temperature for

more than 8 hours), a second bag will be prepared that contains the balance of the planned dose that was not already delivered. The prepared solution should not be frozen.

6.1.6. TRC105 Administration

Patients should be encouraged to drink abundant fluid [e.g., two eight ounce (237 mL) glasses of water or juice] prior to the first treatment. IV hydration prior to and during therapy is left to the discretion of the Investigator, but should be considered for patients that may be volume depleted.

The following TRC105 premedications should be administered 2 hours to 30 minutes prior to the start of each infusion:

- Acetaminophen at a dose of 500 mg to 1000 mg (e.g., 650 mg) p.o. x 1
- Famotidine 20 mg i.v. or p.o. (or similar H2 blocker) x 1. Famotidine (or similar H2 blocker) may be discontinued starting with Cycle 2 in the absence of infusion reactions with the prior dose.
- Cetirizine 10 mg i.v. or p.o. x 1 (or similar oral or intravenous antihistamine). Cetirizine (or similar oral or intravenous antihistamine) may be discontinued starting with Cycle 2 in the absence of infusion reactions with the prior dose.
- Methylprednisolone 100 mg i.v. will be given prior to the Cycle 1 Day 1 and Cycle 1 Day 4 infusions. **In addition, methylprednisolone will be given in the case of a delay of ≥ 10 days between any two scheduled weekly doses, a delay of ≥ 16 days between any two scheduled every other week doses, or if the patient develops an infusion reaction \geq grade 2 during the immediate prior infusion.**

TRC105 premedication, including the methylprednisolone infusion, should be completed 2 hours to 30 minutes prior to initiating TRC105 infusions.

TRC105 will be administered intravenously utilizing an infusion pump. TRC105 has been demonstrated to be compatible with polyethylene lined, non-DEHP infusion sets and polyvinyl chloride, non-DEHP infusion sets. TRC105 is required to be administered with a 0.2 micron downstream filter. The attachment of the infusion pump administration set to the i.v. bag and transport of the TRC105 study drug to the patient will be performed as per standard study site procedures.

Three mg/kg of TRC105 will be administered on cycle 1 day 1 and administered over 4 hours (+/- 15 minutes). Do not increase the infusion rate above 25 mg/min during the Cycle 1 Day 1 dose. The remainder of the cycle 1 dose will be administered on cycle 1 day 4 and infused over a period of 2 hours (+/- 15 minutes). The full TRC105 dose will be administered on cycle 1 day 8 and infused over 1 hour (+/- 15 minutes). Patients must complete at least one 4 hour infusion without the development of any infusion reactions, in order to reduce the subsequent TRC105 infusion to 2 hours (+/- 15 minutes) and complete a 2 hour infusion without the development of any infusion reactions in order to reduce subsequent TRC105 infusions to 1 hour (+/- 15 minutes). Patients with infusion reactions of any kind should be managed appropriately (see [Section 6.1.8](#)) and are not permitted to reduce the duration of the next planned infusion. In the event a dose cannot be completed on a given day, the balance of the planned dose may be administered the following day at the rate of infusion planned for the prior day.

The rate of TRC105 infusion must not exceed 25 mg/min. When the i.v. bag containing TRC105 is empty, flush the i.v. line with a 20 mL normal saline. The dose level, time of transfer to i.v. bag, and the infusion start and stop times must be recorded in the source documents.

TRC105 WEEKLY DOSING: If a patient misses a weekly TRC105 dose and dosing is resumed ≥ 10 days after the last dose, full premedication, including methylprednisolone, should be reinstated as per the initial infusion and first dose should be administered over two days as was done for the initial TRC105 dose.

TRC105 EVERY TWO WEEK DOSING: If a patient misses a TRC105 dose and dosing is resumed ≥ 16 days after the last dose, full premedication, including methylprednisolone, should be reinstated as per the initial infusion and first dose should be administered over two days as was done for the initial TRC105 dose.

TRC105 Every Two Week Dosing:

Patients who received at least 1 cycle of weekly TRC105 may transition to TRC105 administered every two weeks.

The first administration of TRC105 given on an every two week schedule does not need to be split over two days unless there has been delay of ≥ 10 days since the **last weekly infusion**. In this case, TRC105 will be administered over two days with 3 mg/kg administered on day 1 and the remainder on day 4 with full premedication as outlined above.

Doses of TRC105 administered every two weeks will be infused over a minimum of 60 minutes (+/- 15 minutes) for the 15 mg/kg dose and 90 minutes (+/- 15 minutes) for the 20 mg/kg dose. Full premedication will be given 2 hours to 30 minutes prior to the start of the initial two infusion (of TRC105 at either 15 mg/kg or 20 mg/kg) as described above. Premedication (except acetaminophen) may be discontinued in the absence of infusion reaction for subsequent doses (i.e., starting with Cycle 3 Day 1) of TRC105.

Table 12: TRC105 10 mg/kg Weekly Dosing Ideal Schema

	C1D1	C1D4	C1D8	C1D15	C1D22	C2D1+
TRC105 Dose (mg/kg)	3	7	10	10	10	10
Infusion Duration (hours)	4	2	1	1	1	1
Premedication						
Methylprednisolone (mg)	100	100	0	0	0	0
Famotidine (mg)	20	20	20	20	20	0
Cetirizine (mg)	10	10	10	10	10	0
Acetaminophen (mg)	500 - 1000	500 - 1000	500 - 1000	500 - 1000	500 - 1000	500 - 1000

Table 13: TRC105 15 mg/kg Every Two Weeks Dosing Ideal Schema

	C1D1	C1D4	C1D8	C1D15	C1D22	C2D1	C2D15	C3D1+
TRC105 Dose (mg/kg)	3	7	10	10	10	15	15	15
Infusion Duration (hours)	4	2	1	1	1	1	1	1
Premedication								
Methylprednisolone (mg)	100	100	0	0	0	100	100	0
Famotidine (mg)	20	20	20	20	20	20	20	0
Cetirizine (mg)	10	10	10	10	10	10	10	0
Acetaminophen (mg)	500 - 1000	500 - 1000	500 - 1000	500 - 1000	500 - 1000	500 - 1000	500 - 1000	500 - 1000

Table 14: TRC105 20 mg/kg Every Two Weeks Dosing Ideal Schema

	C1D1	C1D4	C1D8	C1D15	C1D22	C2D1	C2D15	C3D1+
TRC105 Dose (mg/kg)	3	7	10	10	10	20	20	20
Infusion Duration (hours)	4	2	1	1	1	1.5	1.5	1.5
Premedication								
Methylprednisolone (mg)	100	100	0	0	0	100	100	0
Famotidine (mg)	20	20	20	20	20	20	20	0
Cetirizine (mg)	10	10	10	10	10	10	10	0
Acetaminophen (mg)	500 - 1000	500 - 1000	500 - 1000	500 - 1000	500 - 1000	500 - 1000	500 - 1000	500 - 1000

6.1.7. TRC105 Dose Reduction/Dose Interruptions

TRC105 dose reductions and interruptions should be avoided in cycle 1. In cycle 2 and beyond, TRC105 dose reductions are allowed for grade 3 or 4 related adverse events that resolve to grade 1 or baseline (including anemia). Dose reductions for other toxicities are allowed at the discretion of the investigator. Treatment dose delays cannot exceed 8 weeks (i.e., both TRC105 and axitinib dosing cannot both be held at the same time for > 8 consecutive weeks if assigned to the combination arm or axitinib cannot be held for > 8 weeks if assigned to axitinib alone arm). However, patients assigned to the combination arm who cannot tolerate axitinib or TRC105 therapy and who demonstrate a response of complete response (CR), partial response (PR) or stable disease (SD) with the combination and are thought to benefit from continued single agent therapy may continue on study on TRC105 or axitinib alone per [Section 5.2](#) of the protocol.

TRC105 and axitinib should be held for two weeks prior and for two weeks following surgical procedures. However, resumption of study treatment can be shorter (but no less than 7 days) or longer than two weeks based on clinical judgement of adequate wound healing and recovery from the procedure.

Table 15: Allowable TRC105 Dose Modifications

Toxicity Attributed to TRC105	Dose Adjustment for Next Dose of TRC105		
	10 mg/kg weekly	15 mg/kg every 2 weeks	20 mg/kg every 2 weeks
Dose Schedule/Level	10 mg/kg weekly	15 mg/kg every 2 weeks	20 mg/kg every 2 weeks
Grade 1 or 2	Maintain Dose Level	Maintain Dose Level	Maintain Dose Level
Grade 3 or 4			
• 1 st appearance	8 mg/kg weekly	12 mg/kg every 2 weeks	16 mg/kg every 2 weeks
• 2 nd appearance	6 mg/kg weekly	10 mg/kg every 2 weeks	12 mg/kg every 2 weeks
• 3 rd appearance	4 mg/kg weekly	8 mg/kg every 2 weeks	8 mg/kg every 2 weeks
• 4 th appearance	Discontinue treatment permanently	Discontinue treatment permanently*	Discontinue treatment permanently*

*After discussion with and agreement of the Sponsor, patients receiving TRC105 every two weeks have the option to return to weekly dosing at the lowest level (i.e., 4 mg/kg weekly), if 8 mg/kg every 2 weeks is not tolerable (i.e., 4th appearance of a Grade 3 or 4 toxicity attributable to TRC105 occurs) and the investigator believes that the patient is receiving benefit from the treatment.

6.1.8. Management of TRC105 Infusion Reactions

If a patient experiences a grade 2 or higher adverse reaction during infusion, the infusion should be interrupted and the patient treated accordingly. Antipyretic, antihistamine, antiemetic, anti-inflammatory, or other symptomatic medications including epinephrine may be administered as indicated. For grade 2 and certain grade 3 infusion reactions, the infusion may be restarted (i.e., the same day) at half of the previous rate if and when the infusion reaction has resolved, and then increased per patient tolerance to a maximum of 25 mg/min. For grade 4 infusion reactions, the infusion should not be restarted and the patient should be discontinued from study treatment.

Infusion reactions will be recorded as AEs in the case report form. Interventions should be documented as concomitant medications or concomitant treatments as appropriate.

Table 16: Management of TRC105 Infusion Reactions

Infusion Reaction Severity	Recommended Management
Grade 1 (mild)	
 1. No intervention 2. Continue infusion unless symptoms worsen
Grade 2 (moderate)	
 1. Interrupt infusion 2. Treat with symptomatic medications^a 3. Resume infusion at half the previous rate when infusion-related symptoms improve to grade 1 or less.
Grade 3 (severe)	
 1. Interrupt infusion 2. Treat with symptomatic medications^a 3. Monitor patient until infusion-related symptoms resolve, including hospitalization if necessary 4. Withdraw patient from study unless other factors that contributed to the infusion reaction are identified and corrected
Grade 4 (life-threatening)	
 1. Discontinue infusion 2. Treat with symptomatic medications^a 3. Hospitalize patient 4. Withdraw from study

^aSymptomatic medications may include but are not limited to diphenhydramine 50 mg i.v. and/or hydrocortisone 100 mg i.v. (for fever, rash, hypoxia, or other hypersensitivity reactions), meperidine 50-100 mg i.v. (for shaking chills/rigors), oxygen by mask or nasal cannula (for hypoxia), epinephrine 0.5 mg i.m. (for hypotension or bronchospasm), albuterol inhaler or nebulizer (for bronchospasm), i.v. fluids (for hypotension), and ondansetron 0.15 mg/kg i.v. (for nausea).

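### Section 6.1.8 and its Table 16 give conflicting rules for restarting TRC105 and for stopping or leaving after the same infusion reaction, so handling can differ between sites

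*Protocol*

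**What the plan says.** The running text of Protocol Section 6.1.8 opens its restart rule with "For grade 2 and certain grade 3 infusion reactions" and continues that "the infusion may be restarted (i.e., the same day) at half of the previous rate if and when the infusion reaction has resolved". For grade 4 it says "the infusion should not be restarted and the patient should be discontinued from study treatment".

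Table 16, in the same section, handles the same grades as follows:
- Grade 2: "Resume infusion at half the previous rate when infusion-related symptoms improve to grade 1 or less".
- Grade 3: interrupt, treat and monitor, then "Withdraw patient from study unless other factors that contributed to the infusion reaction are identified and corrected". No restart step is listed.
- Grade 4: the last step is "Withdraw from study".

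Section 5.2 does not name infusion reactions among its mandatory withdrawals. It does say "DLT does not mandate withdrawal if the DLT resolves and can be treated (i.e., a first dose infusion reaction". It also says that combination-arm patients who cannot tolerate one drug, but have shown CR, PR or SD, "may continue on study on TRC105 or axitinib alone". The synopsis (Duration of treatment) carries the same DLT sentence but limits it to phase 1b patients.

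SAP Section 11.1 censors PFS at the last on-study tumour assessment for a patient taken off study because of toxicity or for any other reason.

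**The concern.** Section 2.3.1.3 counts infusion reactions among the frequent TRC105 toxicities and places most of them at the first dose. Section 2.3.6.1 records a grade 4 vasovagal reaction and a grade 3 myocardial infarction after an infusion reaction. A site facing such an event has two instructions in one section, and they do not agree on when dosing may resume or on what the patient is being removed from.

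Two things are at stake. The first is consistent handling of a safety event. The second is the record of the primary endpoint: whether a patient is labelled off treatment or off study decides whether the SAP censoring rule is triggered. In phase 2 only Arm B receives TRC105, so any effect falls on one arm. Phase 1b patients face the same conflict, without a comparator.

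**Working it through.** **Comparison by grade**

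| Grade | Section 6.1.8 text | Table 16 | Same rule? |
|---|---|---|---|
| 2 | Restart at half rate after resolution | Restart at half rate at grade 1 or less | No: a patient with residual grade 1 symptoms may be restarted only under the table |
| 3 | Same-day restart for some reactions, not defined | No restart step; out of the study unless contributing factors are corrected | Not as written; possibly meant to match, but nothing links them |
| 4 | No restart; off study treatment | Out of the study | No: different exit |

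Other sections do not settle it. Section 6.1.6 refers infusion reactions back to Section 6.1.8. Table 15 gives a dose step at the first grade 3 or 4 TRC105 toxicity, with no exception for infusion reactions.

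**Size of the restart conflict**
- Arm B: 150 patients at 1:1 gives 150/2 = 75.
- Grade 2 reactions at 10 mg/kg with bevacizumab (Section 2.3.2.1): 2/19 = 10.5%.
- 75 × 2/19 = 7.9, about 8 patients.

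This is a ceiling at that rate, because the rules diverge only if grade 1 symptoms persist when restart is considered. The rate itself is an assumption. Table 4 shows 3 grade 2 reactions among the 14 monotherapy patients at 10 or 15 mg/kg (2/3, 0/4, 0/3 and 1/4 by schedule), which would give 75 × 3/14 = 16.

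**Size of the exit conflict**

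The documents give no grade 3–4 rate for TRC105 with axitinib. I assume 1% to 6%:
- Patients affected: 75 × 0.01 = 0.75 to 75 × 0.06 = 4.5.
- Chance of at least one: 1 − 0.99^75 = 53% to 1 − 0.94^75 = 99%.

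The 6% end is close to the one-sided 95% upper bound for 0/48, 1 − 0.05^(1/48) = 6.1%. The 48 pools 19 patients with bevacizumab, 15 in phase 1b at 10 mg/kg and 14 on monotherapy at 10 or 15 mg/kg. It assumes no grade 3–4 reaction where none is reported.

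**Effect on power**
- The plan's 115 events reproduce. Schoenfeld: 4(1.2816 + 0.8416)²/(ln 0.67)² = 113. Freedman: (1.2816 + 0.8416)² × (1.67/0.33)² = 116.
- Power at d events is Φ(√d/2 × |ln 0.67| − 1.2816). At 115 it is 80.7%.
- With 1 to 5 events lost and not replaced, power is 80.4% to 79.3%.

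**Does the exit wording change tumour follow-up?**

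At grade 3 it can: one reading keeps the patient dosed and scanned every 56 days, the other removes the patient. At grade 4 it changes little. The Arm B End of Study visit falls within 7 (± 1) days of the last dose (Table 10, note 3), and Section 4.1.4 lists no imaging after treatment. For a first-dose exit, a screening scan up to 28 days earlier is at most 28 + 8 = 36 days old at that visit, inside the 8-week allowance, so no new scan need be taken under either wording. What remains is the request in Section 7.1.3.1, in a note on global deterioration, to try to document progression after treatment ends.

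**The case against.** The strongest reply is that this is loose wording with little effect. Table 16 is headed as recommendations and the text is permissive, so sites have discretion in any case. The undefined grade 3 subset may simply be the patients covered by the table's exception. The two bevacizumab-study patients needed only a brief interruption, so few restarts would differ in practice. The three grade 3 reactions in the monotherapy study all occurred at 0.3 to 1 mg/kg, with TRC105 undetectable in serum at dosing, and none at 10 or 15 mg/kg. Phase 2 adds steroid premedication and a split first dose.

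Much of this stands. It limits the claim to handling that can differ, makes about 8 a ceiling at the 2/19 rate, and rules out projecting 3/50 onto Arm B. It does not remove the grade 2 and grade 4 contradictions. At grade 3 the proposed match is a guess that the protocol never states.

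A reader might also infer that the DLT sentence in Section 5.2 creates a further conflict for randomised patients. The documents do not support that. The synopsis limits the sentence to phase 1b, DLT is defined only in the phase 1b overview, and the phase 2 overview has no DLT rule. The fault is only that Section 5.2 omits the limit.

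**Conclusion.** The contradiction is real at grades 2 and 4. At grade 3 it is an unresolved mismatch. The consequence is that sites can handle a common, mainly first-dose toxicity differently. At the 2/19 rate, at most about 8 of 75 Arm B patients would meet the restart conflict. The exit conflict probably touches few: 0.75 to 4.5 under an assumed 1% to 6%, which the documents neither confirm nor exclude.

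A reader might infer that the exit wording alone decides PFS follow-up and so damages the primary comparison. That goes too far. At grade 4 scheduled scans largely end under either wording, because the protocol has no post-treatment imaging in either arm. The grade 3 contrast could produce censoring in Arm B only, but on these assumptions power stays at or above 79.3% against 80.7%, so no material loss is claimed. The case for acting rests on inconsistent safety instructions and an unclear exit term, and the correction is cheap.

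**What to change.** Reconcile the Section 6.1.8 text and Table 16 to one restart criterion and one exit rule for each grade. At grade 3, either define the subset that may restart or tie it explicitly to the table's exception. This review does not say which rule is right. Use *stop study treatment* and *leave the study* as distinct terms throughout, align Section 5.2 with the result, and mark its DLT sentence as applying to phase 1b.

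If the sponsor states that the 56-day tumour assessments continue after treatment stops, the statement should apply in both arms and to every reason for stopping short of withdrawn consent. A rule for infusion-reaction patients alone would operate only in Arm B and make PFS ascertainment unequal. The SAP Section 11.1 censoring rule for patients taken off study should be aligned with whatever is decided.

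The cost is protocol wording, a site memo and, if follow-up is extended, some additional scan visits.
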